#### **10.1.2.2 Visit 4, 6, 8, 10, 12/Month 1, 6, 12, 18, 24 (Day 30, 180, 360, 540, 720)**

Patients will receive either placebo or venglustat, orally, at the clinic.

Patients will be instructed to record any missing doses and pain medication used in their diary. The patient should bring their diary and any remaining capsules to each clinic visit. The site staff will review the patient diary during each clinic visit and record excursions from treatment into the eCRF.

The following activities will be performed:

- Whenever possible, the following scales and questionnaires should be done prior to clinical interaction with the Investigator:
  - BDI-II (Visits 6, 8, 10, 12),
  - BPI (Visits 4, 6, 8, 10, 12),
  - BFI (Visits 4, 6, 8, 10, 12),
  - PGIS (Visits 8, 10, 12),

- PGIC (Visits 8, 10, 12),
- EQ-5D-5L (Visits 6, 8, 10, 12).
- Review of concomitant medications.
- Review of current medical conditions, with AE/SAE reporting (if any).
- Collection of spot urine sample.
- Collection of home urine based on 24-hour collection.
- Review daily symptom diary for completeness.
- Review of missed dose log for compliance.
- Abbreviated physical examination (focus on areas important for assessment of AEs if necessary; Visits 4, 6, and 8).
- Complete physical examination at Visits 10 and 12.
- Record of body weight measurement at Visit 8.
- Vital signs.
- 12-lead ECG at Visits 6 and 12.
- Laboratory assessments.
  - Chemistry and hematology.
- Blood sampling for GSL markers.
- Blood sampling for biomarker analysis (not collected at Month 1 in Stage 2).
- Blood sampling for PK analysis:
  - Stage 1: pre-dose and 3 hours post-dose at Visit 4; pre-dose at Visits 6 and 10,
  - Stage 2: pre-dose and 3 hours post-dose at Visit 4; pre-dose at Visit 12.
- Biobanking blood sample (optional) at Visits 8 and 12.
- Urinalysis (local dipstick test) including glucose, protein, bilirubin, urobilinogen, pH, specific gravity, blood, ketones, nitrite, and leukocyte esterase. Central urinalysis will be performed if any abnormality is observed in the urinalysis dipstick test.
- Urinalysis with microscopy; (to be performed by a central laboratory).
- Ophthalmological examination
  - At Month 6 (Visit 6), Month 12 (Visit 8), Month 18 (Visit 10), and Month 24 (Visit 12): ophthalmological examination with pupil dilation
  - At Month 12 (Visit 8), Month 18 (Visit 10) and Month 24 (Visits 12) in Stage 1, and at Month 12 (Visit 8) and Month 24 (Visits 12) in Stage 2, ophthalmological examination will also include measurement of the corneal thickness (or endothelial cell density) and measurement of intraocular pressure.

- MRI at:
  - Stage 1: Visits 4 and 10,
  - Stage 2: Visit 10.
- Urine pregnancy test (for WOCBP).
- If the patient is participating in the mGFR substudy, perform iohexol infusion and collect blood samples according to [Appendix L](#), at Visits 8 and 12.
- Dispense study medication at Visits 4, 6, 8, and 10.
- Remind the patient that the patient daily symptom diary should be completed daily until Visit 5 and for 7 days before Visit 8.

Remind patient to return to the clinic for next visit, bring their diaries and any remaining capsules.

Provide WOCBP with at-home pregnancy tests and remind them to administer the pregnancy test monthly between visits.

Remind patient to not take the dose at home on the clinic visiting day at Visits 6 and 10 during Stage 1, and at Visit 12 during Stage 2.

The patient should be given suitable containers in which to collect the spot urine, to be returned at that visit (see [Section 9.4.3](#)).

#### **10.1.2.3 Visit 5, 7, 9, 11/Month 3, 9, 15, 21 (Day 90, 270, 450, 630)**

Patients will receive either placebo or venglustat, orally, at the clinic.

Patients will be instructed to record any missing doses and pain medication used in their diary. The patient should bring their diary and any remaining capsules to each clinic visit. The site staff will review the patient diary during each clinic visit and record excursions from treatment into the eCRF.

The following activities will be performed:

- Whenever possible, the following scales and questionnaires should be done prior to clinical interaction with the Investigator:
  - BDI-II ([Appendix D](#)),
  - BPI ([Appendix E](#)),
  - BFI ([Appendix F](#)),
  - PGIS (Visit 5 only; [Appendix G](#)),
  - PGIC (Visit 5 only; [Appendix H](#)),
  - EQ-5D-5L (Visit 5 only; [Appendix I](#)).
- Review of concomitant medications.

- Review of current medical conditions, with AE/SAE reporting (if any).
- Collection of spot urine sample.
- Review daily symptom diary for completeness.
- Review of missed dose log for compliance.
- Abbreviated physical examination (focus on areas important for assessment of AEs if necessary).
- Vital signs.
- Laboratory assessments.
  - Chemistry and hematology.
- Urinalysis (local dipstick test) including glucose, protein, bilirubin, urobilinogen, pH, specific gravity, blood, ketones, nitrite, and leukocyte esterase. Central urinalysis will be performed if any abnormality is observed in the urinalysis dipstick test.
- Urinalysis (microscopy; to be performed by a central laboratory).
- Urine pregnancy test (for WOCBP).
- MRI (at Visit 7 of Stage 1).
- Dispense study medication.
- Remind the patient that the patient daily symptom diary should be completed for the 14 days before Visit 10 and Visit 12.

Remind patient to return to the clinic for next visit, bring their diaries and any remaining capsules.

Provide WOCBP with at-home pregnancy tests and remind them to administer the pregnancy test monthly between visits.

The patient should be given a suitable container in which to collect the 24-hour urine and the spot urine, required prior to the next visit and to be returned at that visit.

### **10.1.3 Follow-up visit - Visit 13/Month 25 (Day 750)**

Not applicable for patients who may be eligible for a potential long-term extension study after completion of 24 months of treatment.

**Visit window:** The Follow-up Visit (Day 750) can be performed within a -7 to +21 days window.

The following activities will be performed:

- Review of current medical conditions, with AE/SAE reporting (if any).
- Review of current and prior medications.
- Collection of spot urine sample.

- Abbreviated physical examination (focus on areas important for assessment of AEs if necessary).
- Record of body weight measurement.
- Vital signs.
- Laboratory assessments (Chemistry only).
- Blood sampling for GSL markers.
- Blood sampling for biomarker analysis in Stage 1. In Stage 2, only if to be done following analysis of Stage 1 samples.

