
DURATION OF STUDY PERIOD (per patient)
	
Stage 1
 
Total study duration: 26 months (maximal).
 
 
• Screening period: 
 
- Initial screening: up to 15 (+3) days.
 
- Placebo run-in period: 15 days ±3 days.
 
 
 
• Core treatment period: 24 months.
 
• Follow-up: 30 days after final dose of IMP. Not applicable for patients who may be eligible for a potential long-term extension study after completion of 24 months of treatment.
 

	
Stage 2
 
Total study duration: 26 months (maximal).
 

• Screening period:

- Initial screening: up to 15 (+3) days.

- Placebo run-in period: 15 days <math>\pm</math>3 days.

• Core treatment period: 24 months.

• Follow-up: 30 days after final dose of IMP. Not applicable for patients who may be eligible for a potential long-term extension study after completion of 24 months of treatment

--	---

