- b 30 days after the last dose of IMP will be evaluated. Not applicable for patients screening for the long-term extension study within 30 days after Month 24 (Visit 12). For patients to be screened for the long-term extension study after Month 24 (Visit 12) and prior to Month 13 (Visit 13), the last visit in Study EFC15392 should coincide with the first visit in the long-term extension study.
- c Height to be measured only at Visit 1.

- d* Vital sign measurements (sitting BP and heart rate): For all measurements 3 separate seated BP measurements should be taken with at least 1 minute between readings, following at least 10-minute rest period and prior to phlebotomy. The arm with the higher pressure at the initial screening visit should be used for all subsequent BP measurements.
- e* The abbreviated physical examination should focus on areas important for assessment of AEs if necessary.
- f* All laboratory assessments occur prior to intake of double-blind IMP. Samples should be collected in fasting conditions. Some assessments done at the beginning of screening may have to be repeated, Investigator will need to receive and evaluate results of repeated tests prior to Visit 3.
- g* Serum pregnancy testing only at Visit 1; urine pregnancy testing subsequently. Serum pregnancy test results must be reviewed prior to the run-in phase for all WOCBP unless there is documented history of menopause (based on documented FSH and estradiol levels - if results not documented then FSH and estradiol will be tested at screening) or they are surgically sterile. Any positive urine test results must be confirmed based on serum pregnancy test. The Investigator may perform additional tests at their discretion or as required by local regulations. Patients will perform monthly urine pregnancy at home and report to the site.
- h* Viral serology (central lab) includes hepatitis B surface antigen (HBs Ag), hepatitis B core antibody (HBc Ab) anti-hepatitis C virus (anti-HCV) antibodies, anti-human immunodeficiency Virus 1 and 2 antibodies (anti-HIV1 and anti-HIV2 Ab).

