- q* The daily diaries will be filled out by patients at home for 7 days prior to baseline visit and after that at home for consecutive days for the specified administration period before the study visits and will be collected at the time of visit.
- r* The PROs will be administered to patients at study visit according to the listed schedule.
- s* Prior to the start of IMP at Baseline Visit. In subjects who have consented to it, samples of serum will be collected and archived for future analysis.

- t* All SAEs, AEs and AEs of special interest (AESIs) will be collected starting with signing informed consent and continue until 30 days after the last dose of IMP or study end, whichever comes later. All AEs that occurred during treatment should be followed for at least 30 days following the last dose of IMP or until the event has resolved, the condition has stabilized, the etiology of the event is determined to be not related to IMP, or the patient is lost to follow-up. All patients should be followed to collect safety information up to 30 days after the last IMP administration or up to the first visit of the long-term extension study, whichever occurs first. For patients enrolled or screened into the long-term extension study prior to 30 days after the last dose of IMP, all SAEs, AEs, and AESIs will be collected up to the last visit in Study EFC15392, which will coincide with the first visit in the long-term extension study. Details of ongoing AEs and ongoing medications at the time of the last visit in Study EFC15392 will be duplicated as such into the long-term extension study.
- u* The initial screening period (Visit 1) can last up to 15 days (+3 days). Visit 2 can be performed as soon as results of all assessments performed at Visit 1 are available.
- v* During the run-in period the patient will receive single-blind placebo.
- w* At Visit 12 patients may be offered to enter long-term extension study. For patients who will agree and will be eligible to enter into a potential long-term extension study without any discontinuation between the EFC15392 and the LTS15823 studies, Visit 12 (end of treatment visit) of EFC15392 study will correspond to Visit 1 of LTS15823 study including all planned evaluations to be performed at Visit 12 of EFC15392 study and an additional MRI that will be performed in the frame of Visit 1 of the LTS15823 study.

#### 1.4 STUDY FLOW CHART FOR STAGE 2

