- a If a patient discontinues treatment with IMP early during the core treatment period, the patient will have an End-of-Treatment/Early Withdrawal (EOT/EW) Visit within 7 days and a Follow-up Visit 30 days after the last dose of IMP. In addition, every effort will be made to have the patients return to the site at the time corresponding to their scheduled visits, particularly the Month 24 Visit. If the patient does not agree to a site visit, they will be contacted by telephone to inquire about safety status.
- b 30 days after the last dose of IMP will be evaluated. Not applicable for patients screening for the long-term extension study within 30 days after Month 24 (Visit 12). For patients to be screened for the long-term extension study after Month 24 (Visit 12) and prior to Month 13 (Visit 13, the last visit in Study EFC15392 should coincide with the first visit in the long-term extension study.
- c Height to be measured only at Visit 1.
- d Vital sign measurements (sitting BP and heart rate): For all measurements 3 separate seated BP measurements should be taken with at least 1 minute between readings, following at least 10-minute rest period and prior to phlebotomy. The arm with the higher pressure at the initial screening visit should be used for all subsequent BP measurements.
- e The abbreviated physical examination should focus on areas important for assessment of AEs if necessary.
- f Serum pregnancy testing only at Visit 1; urine pregnancy testing subsequently. Serum pregnancy test results must be reviewed prior to the run-in phase for all WOCBP unless there is documented history of menopause (based on documented FSH and estradiol levels - if results not documented then FSH and estradiol will be tested at screening) or they are surgically sterile. Any positive urine test results must be confirmed based on serum pregnancy test. The Investigator may perform additional tests at their discretion or as required by local regulations. Patients will perform monthly urine pregnancy at home and report to the site.
- g Viral serology (central lab) includes hepatitis B surface antigen (HBs Ag), hepatitis B core antibody (HBc Ab) anti-hepatitis C virus (anti-HCV) antibodies, anti-human immunodeficiency Virus 1 and 2 antibodies (anti-HIV1 and anti-HIV2 Ab).

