## **6.2 DURATION OF STUDY PARTICIPATION**

### **6.2.1 Duration of study participation for each patient**

The maximum study duration per patient will be approximately 26 months.

This will consist of a screening period of up to 30 +3 days (initial screening period of up to 15 +3 days and single-blind placebo run-in period of 15 ±3 days), followed by a blinded study core treatment period of 24 months and a 30-day follow-up visit (for patients not participating in the potential long-term extension study) after the final dose of investigational medicinal product (IMP).

Patients who completed 24 months of treatment in EFC15392 study may be given the option to enroll into an open-label long-term extension study LTS15823 (additional 24 months of treatment with 15 mg venglustat [ie, as specified in the EFC15392 protocol the dose selected for Stage 2 of EFC15392 study during unblinded review by the DMC of the aggregated safety data for 150 patients who have completed at least 1 month of treatment in EFC15392 study]).

The last study visit:

1. for patients who elect to enter the potential long-term extension study upon completion of 24 months of treatment in EFC15392 study will be Visit 12 (Month 24)
2. for patients who complete the treatment in EFC15392 study and elect not to enter this potential extension study will be Visit 13 (Month 25)
3. for patients who permanently discontinue medication and continue for all the remaining visits will be Visit 12 (Month 24) if they continue for all the remaining visits, or it will be their premature follow-up visit.

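### The protocol gives three incompatible rules for which completers attend the 30-day off-drug visit (Visit 13), and its wording on the end of safety collection is not aligned

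*Protocol*

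**What the plan says.** **Who has Visit 13.** Three rules are in current text.

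- *Eligibility.* Section 10.1.3 sets out the visit and opens by exempting a group: "Not applicable for patients who may be eligible for a potential long-term extension study after completion of 24 months of treatment". The clinical trial summary, under duration of study period, says the same for both stages: "Follow-up: 30 days after final dose of IMP. Not applicable for patients who may be eligible for a potential long-term extension study".
- *Screening.* Footnote b of the Stage 1 and Stage 2 flow charts (1.3 and 1.4) reads: "Not applicable for patients screening for the long-term extension study within 30 days after Month 24 (Visit 12".
- *Participation.* Section 6.2.1 describes "a 30-day follow-up visit (for patients not participating in the potential long-term extension study) after the final dose". Its list of last visits adds that completers who choose not to go into the extension finish at Visit 13, and that those who choose to enter finish at Visit 12.

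**When safety collection ends.** Footnote t of both flow charts starts with collection that should "continue until 30 days after the last dose of IMP or study end, whichever comes later". A later sentence, addressed to all patients, follows them to 30 days after the last dose or to the first extension visit, whichever is first. A further sentence begins "For patients enrolled or screened into the long-term extension study prior to 30 days after the last dose of IMP" and ends their collection at the last visit of this study, which is also the first extension visit.

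**Treatment-emergent window.** Section 9.2.3 and the endpoint entries of the summary run the treatment period to 30 days after the last dose, with no mention of the extension. Section 11.4.3 and SAP 4.1 end it earlier if the first extension visit comes first.

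**A slip.** Footnote b refers to screening "after Month 24 (Visit 12) and prior to Month 13 (Visit 13), the last visit in Study EFC15392 should coincide with the first visit". Visit 13 is Month 25 everywhere else.

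**The concern.** Eligibility, being screened and taking part are different conditions, and they pick out different patients. A site will usually work from the section that lists a visit's procedures, or from the flow chart. Section 10.1.3 and footnote b are those two places, and neither carries the 6.2.1 rule.

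For a completer who receives no extension drug, Visit 13 is the scheduled check 30 days off treatment. It comprises chemistry, vital signs, weight, an abbreviated examination, spot urine, glycosphingolipid markers, and review of adverse events and medication. The chemistry panel includes ALT (9.4.7), and an ALT increase is an adverse event of special interest (10.4.1.3). Section 10.4.2 does not resolve the matter: it runs adverse event recording to the patient's protocol-defined end of study, which depends on which Visit 13 rule applies.

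**Working it through.** No planned figure is involved, so the check is a comparison of texts followed by a day count.

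**Step 1. Apply each Visit 13 rule to each kind of completer.**

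| Completer | 10.1.3 and summary | Footnote b | 6.2.1 |
|---|---|---|---|
| Rolls directly into LTS15823 | waived | waived | waived |
| Clearly ineligible, not screened | required | required | required |
| Eligible, declines, never screened | **waived** | required | required |
| Screened within 30 days of Month 24, does not enter | waived if thought possibly eligible | **waived** | required (not participating) |

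The rules agree in the first two rows and conflict in the last two. In the last row, 6.2.1 is not fully tidy either. Its list sorts patients by their choice to enter, so someone who chooses to enter and then fails extension screening is caught only by the general words about not participating.

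**Step 2. Put the end-of-safety rules side by side.** Take the last dose at Day 720 and the first extension visit d days later. The documents do not give d, so a range is shown. It starts at 1 because footnotes w and y equate Visit 12 with the first extension visit only for patients who agree, are eligible and roll over without a gap.

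- Footnote t, opening sentence: Day 720 + 30 = Day 750, or study end if later.
- Footnote t, later sentences: Day 720 + d when d is below 30.
- Section 9.2.3 and the summary: treatment period to Day 750.
- Section 11.4.3 and SAP 4.1: treatment-emergent period to the earlier of Day 750 and Day 720 + d.

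The gap between the longer and shorter wordings is 30 − d days:

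| d (days) | 1 | 7 | 14 | 21 | 30 |
|---|---|---|---|---|---|
| 30 − d (days) | 29 | 23 | 16 | 9 | 0 |

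This measures how far the texts differ. It does not count days of data lost or reclassified.

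**Step 3. See who is outside the problem.** Patients who stop treatment early have a premature follow-up visit with all Visit 13 procedures (10.3.4). Events that began on treatment are still followed (footnote t). Serious events judged related to study drug remain reportable after the patient's end of study (10.4.3). A decliner who is never screened has no first extension visit, so the treatment-emergent window stays at last dose plus 30 days; only the visit is at risk.

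**The case against.** The case for leaving the text alone has four parts.

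1. *The intended rule is visible.* Section 6.2.1 states it, and footnote b also keeps the visit for a decliner who is never screened. This stands as evidence of intent. It does not help a site that reads 10.1.3, which says the opposite for an eligible decliner.

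2. *Footnote t is a general rule with a specific exception.* Its later sentences, 11.4.3 and SAP 4.1 all stop at the first extension visit. This largely stands, and the SAP settles the reported window. What remains is that the later-of and earlier-of sentences are both stated for everyone, and that 9.2.3 and the summary were not brought into line.

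3. *There is still a contact after treatment.* Under footnote b, a patient screened after Month 24 is seen at the first extension visit. This is true, but that visit can fall well before day 30. Its procedures are in a protocol that is not among these documents.

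4. *Few patients are involved.* Both studies were discontinued after the futility analysis. The SAP reports no post-baseline MRI in Stage 2, where the first is due at Month 18, so Stage 2 completers are very unlikely. This stands.

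A reader might go further and infer that up to 29 days of events per patient would move from the treatment-emergent tables to the post-treatment overview. The documents do not support that. Under the later sentences of footnote t, collection in this study stops at the same visit as the treatment-emergent period, so no newly collected events are left to reclassify. The shift arises only if a site collects under footnote t's opening sentence while the analysis applies SAP 4.1. Whether LTS15823 would record later events cannot be checked.

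**Conclusion.** The inconsistency is real and minor. Three incompatible Visit 13 rules are in force. Read literally, 10.1.3 and the summary omit the visit for an eligible decliner, and footnote b omits it for a patient who is screened but does not enter. The loss is at most one scheduled safety visit per such completer. The end-of-collection sentences in footnote t and the treatment period in 9.2.3 and the summary also need aligning, although the analysis window is already fixed by the SAP.

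The number of patients cannot be derived, because extension entry criteria, entry rates and last-dose dates are not given. That it is small is a judgement, based on both studies having stopped. Efficacy analyses, power and type I error are untouched.

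It would also be too strong to say that the cut-off must be the first extension dose instead of the first extension visit. For patients who do enter, that is a design choice which the plan makes consistently in footnote t's later sentences, 11.4.3 and the SAP.

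**What to change.** - **Visit 13.** In 10.1.3, the summary's duration entry and both footnotes b, replace the exemption with the 6.2.1 rule. The visit is required for every completer who does not enter LTS15823, including those who decline and those who fail extension screening, and is waived only for patients who enter. If entry is undecided when the visit is due, do it before any first extension dose; this matters because the visit window runs from −7 to +21 days. Add the same clause to the list in 6.2.1.
- **Safety collection.** In both footnotes t, keep the opening sentence as the general rule. Limit the first-extension-visit cut-off to patients who actually enter LTS15823. State that patients screened but not entered are followed to last dose plus 30 days. For entrants, the hand-over of ongoing events and medications at that visit is unchanged.
- **Treatment-emergent period.** Put the same limit in 11.4.3 and SAP 4.1, and cross-refer 9.2.3 and the summary's endpoint entries to 11.4.3.
- **Slip.** In both footnotes b, change Month 13 to Month 25 for Visit 13.

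The cost is wording in those places and one SAP sentence. Visit 13 is already in the schedule. The analysis would need to know which patients entered LTS15823. Moving the cut-off to the first extension dose for entrants is optional and not needed here.
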